14.3 Risk/Benefit Analysis

The potential procedural risks and the minimal interventional risk are outweighed by the likely benefit of improvement of radiation-induced xerostomia. The procedural risks will be minimized by the use of a skilled practitioner injecting all MSCs under ultrasound guidance. The subjects will be observed for 30 minutes after MSC injection to ensure no acute systemic reaction has occurred.

There have been no SAEs or DLTs occurring within 1 month of MSC injection (primary objective), supporting the safety and low risk of MSC injection into a submandibular gland. Additionally, the cryopreserved MSCs that will be utilized for the second injection are identical to the MSCs used for the first injection. The stability of the cryopreserved MSCs has been validated by the PACT GMP facility. MSCs for the second injection will undergo the same quality control process and will have the same release criteria as the MSCs for the initial injection. There is a very small risk that the cryopreserved MSC IMP used for the second injection is not as effective as the MSC IMP used for the first injection. Additionally, the second injection should carry with it the exact same, very small, risk for infection, bleeding, etc. detailed above. There is no known increased risk in the second injection of MSC IMP as compared to the first injection. The likely benefit of an improvement in radiation-induced xerostomia is increased when MSCs are injected into both submandibular glands to allow for optimal tissue recovery. Injecting both submandibular glands has the proposed benefit of allowing both salivary glands to recover and repopulate, leading to reduced xerostomia and improved quality of life.

15.0 ADVERSE EVENTS REPORTING REQUIREMENTS

15.1 Overview of Adverse Event Reporting

Adverse event data collection and reporting, which are required as part of every clinical trial, are done to ensure the safety of patients enrolled in the studies as well as those who will enroll in future

studies using similar agents. Adverse events are reported in a routine manner at scheduled times during a trial. Additionally, certain adverse events must be reported in an expedited manner to allow for optimal monitoring of patient safety and care. The first step is to identify the event using the Common Toxicity Criteria for Adverse Events (CTCAE). The severity of the event should then be graded using the CTCAE criteria. Next, it must be determined if the adverse event is related to the study treatment (attribution). If so, determine whether the adverse event is expected or unexpected. Using this information and the adverse event reporting section of the protocol, it can be determined whether an adverse event should be reported in an expedited report or a routine report.

15.2 Common Terminology Criteria for Critical Adverse Events (CTCAE)

The CTCAE document provides descriptive terminology for adverse event reporting. A grading (severity) scale is provided for each adverse event term. This study will utilize version 5.0 of the CTCAE of the National Cancer Institute for toxicity and performance reporting. A copy of the CTCAE version 5.0 can be downloaded from the NCI website at:

http://ctep.cancer.gov/protocolDevelopment/electronic_applications/ctc.htm

15.3 Definition of Adverse Event

An **adverse event** (AE) is defined as any untoward medical occurrence in a patient receiving study treatment and which does not necessarily have a causal relationship with this treatment. An AE can therefore be any unfavorable and unintended sign (including an abnormal laboratory finding), symptom, or disease temporally associated with the subject's participation in the research, whether or not considered related to the subject's participation in the research.

15.4 Grading the Severity of Adverse Events

Guidance for grading each type of event is found in the CTCAE. Assessment of severity is frequently subjective and medical judgment should be used to compare the reported adverse events to similar types of events observed in clinical practice. **It is important to recognize that severity is not equivalent to event seriousness**; severity is a measure of intensity; thus, a severe event may not necessarily be classified as a serious event. Definitions of the grading categories to assess severity of adverse events are as follows:

- **Mild** (grade 1): the event causes a sign or symptom barely noticeable to the patient without disruption of normal daily activities
- **Moderate** (grade 2): the event causes sufficient discomfort to interfere with normal daily activities and may require treatment of symptoms
- **Severe** (grade 3): an event of sufficient severity to cause the patient severe discomfort and leaving the patient unable to perform normal daily activities; Symptoms may be resistant to conventional symptomatic treatment.
- **Life threatening** (grade 4): the patient was at risk of death at the time of the event.
- **Fatal** (grade 5): the event caused death.

15.5 Causality/Attribution

The causality, or attribution, of AEs refers to the relationship of the AE to the experimental intervention (IMP). The investigator, using the following points, makes the assessment of whether there is a reasonable possibility of a causal relationship:

- Timing of the event between administration of IMP and the onset of adverse event
- Dose of IMP and evidence, if any, of overdose

- A known or expected response pattern to the suspected IMP based on previous experience
- Physiological effects/pharmacological action of the IMP
- Adverse events known to occur with the IMP belonging to the same or a similar class
- Specific genetic predisposition of the patient

Based on the aforementioned points, the PI assigns attribution of the adverse event to the study treatment. Attribution categories are as follows:

- Definite: The AE is clearly related to the study treatment
- Probably: The AE is likely related to the study treatment
- Possible: The AE may be related to the study treatment
- Unlikely: The AE is doubtfully related to the study treatment
- Unrelated: The AE is clearly NOT related to the study treatment

15.6 Seriousness of Adverse Event

Adverse events that meet one or more of the following are classified as serious:

- Results in death
- Is life-threatening
- Requires inpatient hospitalization or prolongation of existing hospitalization (for > 24 hours)
- Results in persistent or significant disability or incapacity
- Produces a congenital abnormality or birth defect
- a medical event, based on appropriate medical judgment, that is believed to jeopardize the patient and/or requires medical or surgical intervention to prevent one of the outcomes defining a SAE. For example: allergic bronchospasm requiring intensive treatment in an emergency room or at home, convulsions that may not result in hospitalization.

15.7 Determination of Expectedness

Expected events are those that have been previously identified as resulting from administration of the intervention. An adverse event is considered unexpected, for expedited reporting purposes only, when either the type of event or the severity of the event is **not** listed in:

- Current known adverse events listed in this protocol
- Investigator Brochure (for agents provided under an IND)

15.8 Recording Adverse Events

- All adverse events regardless of attribution will be recorded from the time of the research blood draw through the 1 month post MSC injection visit.
- Diagnostic and therapeutic non-invasive and invasive (i.e., surgical) procedures will not be reported as adverse events. However, the medical condition for which the procedure was performed must be reported if it meets the definition of an adverse event, unless the condition existed prior to the patient's MSC IMP injection.
- If an AE is determined to be caused by the IMP (definitely related) or associated with the IMP (probably related or possibly related), and is a CTCAE v5.0 grade 3 or higher, it will be reported regardless of the timeframe of the occurrence.

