9.0 STUDY TREATMENT

9.1 Description of the Investigational Medicinal Product (IMP)

Drug Substance:

Autologous bone marrow-derived MSCs at a concentration of 10×10^6 cells/mL

Drug Product (IMP):

Suspension of autologous bone marrow-derived MSCs suspended in a solution of Plasmalyte A containing 0.5% human serum albumin. Cells will be administered at one dose level, Dose 0, with a possible lower dose if the DLT criterion is reached. For each cell dosage we have set a 20% acceptable deviation. Dose levels and acceptable ranges (in parentheses) are as follows:

- Dose -1: $5 (4 - 6) \times 10^6$ MSCs (into one submandibular gland; to be used only if Dose level 0 is not tolerated)
- Dose 0: $10 (8 - 12) \times 10^6$ MSCs (into one submandibular gland)

If the MSC IMP is not administered to the patient due to a failure of the MSCs to expand to achieve the required dose/ or the MSC IMP does not pass QA testing, the subject will be withdrawn from study, and followed for 1 month post the aspiration procedure to ensure AE/SAEs are appropriately recorded. These subjects will be replaced in the study by the recruitment of another subject.

Route of administration: injection into one submandibular gland (must have 2 glands present). The gland selected will be the gland that received the lower radiation dose. The contralateral gland of each interested subject will be injected with autologous MSC IMP at Dose level 0 following completion of the primary objective with no DLTs reported.

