9.10 Study Procedural Intervention(s) Description

Pre-Intervention Bone Marrow Biopsy for MSC Collection

Each subject will undergo a bone marrow (BM) aspirate in order to obtain MSCs. Subjects will undergo BM aspiration for the collection of approximately 30 mL of BM aspirate in the UW Oncology Clinic by an experienced practitioner. Female subjects will have a urine pregnancy test which must be negative to participate. An IV will be placed for conscious sedation, if needed, and for blood collection following the aspiration procedure. If conscious sedation is chosen by the patient, IV sedative will be administered by a trained nurse who will monitor the subject throughout the procedure and recovery from sedation. For the BM collection procedure, the subject will be placed in a prone or side-lying position and the area over iliac crest will be anesthetized with a local anesthetic. The skin will be scrubbed with chlorhexadine and draped with sterile towels/drapes. Using sterile technique, the physician will insert a harvesting needle and aspirate BM into 2-4 10cc syringes, previously rinsed with 3000 units of heparin, collecting 5-10 ml at a time. After the first syringe is aspirated, the beveled needle may be turned 90 degree for three more turns and the aspiration repeated after each turn. Each syringe filled with bone marrow will be injected into a tube that has been prepared with Na Heparin. The collection tube will be labeled with a unique hMSC bank ID number. When all BM has been collected the harvesting needle will be removed and a dressing will be placed over the aspiration site. If subjects have received intravenous (IV) sedation, they will be observed for at least 1 hour or until fully recovered. In addition, subjects will receive a phone call from the research study coordinator within 3 +/- 2 days to review any potential side effects that might be attributable to the bone marrow aspiration.

MSC IMP Administration

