11.7 Biobanking of Blood Sample

Biobanking of participant blood will occur at a baseline visit or the day of the bone marrow aspiration, and at the 1 (for those seen at 1 month), 3, 6, 12, and 24 month visits. Approximately 3 mL of blood will be placed into an EDTA tube which will be transported to the [name] lab, in WIMR where it will be stored in a secure freezer in a secure location. Future clinical studies on the biobanked blood may include measuring inflammatory cytokines or other immune markers.

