12.3 Retention for Future Research: Data & Biospecimen Banking

Purpose of Storage

The purpose of collecting and storing biospecimens is to establish a biobank for use by UW-Madison researchers to use who are investigating the causes, diagnosis, prevention and treatment of cancer.

Data and/or Biospecimens Being Stored

Blood in a 3 mL standard EDTA tube will be collected from each participant on the day of bone marrow biopsy, and at the 1(for those seen at 1 month), 3, 6, 12, and 24 month follow-ups. This blood will be labeled with a unique subject ID code. All tubes of blood will then be stored in a secure freezer in the secured [name] lab in WIMR.

Saliva will be collected from each participant at the pre-specified timepoints as detailed previously. The saliva will be used for clinical endpoints as detailed previously, any remaining saliva will be stored in an Eppendorf tube in a secure freezer in the secured [name] lab in WIMR.

Location of Storage

Blood and saliva tubes labelled with coded subject ID number, date, and time point, will be stored in the [name] Laboratory. Data associated with the blood and saliva tubes is on a UW password-protected server.

Duration of Storage

Biospecimens will be stored until they are used up in their entirety.

Access to Data, Images, Recordings and/or Biospecimens and Security Measures

UW researchers who are doing biomedical research may apply for access to coded data and blood (no patient identifiers on tube).

Procedures to Release Data or Biospecimens

Researchers must have local IRB approval for their study which will include study of the biospecimens and accompanying data.

Process for Returning Results

There are no plans to disclose results of future testing to research subjects.

Process for Tracking Subject Consent and Authorization

In the consent form for this study, subjects are informed of an optional aspect of the study that involves donating blood for future biomedical research. Subjects are made aware they do not have to donate biospecimens to the Biobank to participate in the study. Subjects must opt into the biobanking aspect of the study by checking a box and initialing a line next to the box.

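### Section 15.8 does not reliably capture adverse events from the marrow harvest, and conflicts with the sections that do collect them

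*Combined protocol and SAP*

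**What the plan says.** Three parts of the plan set what is kept.

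- **Start of recording.** Section 15.8, first bullet: "All adverse events regardless of attribution will be recorded from the time of the research blood draw", up to the one-month visit after injection. The draw is not defined there or elsewhere.
- **Procedure carve-out.** Section 15.8, second bullet: a procedure is not itself an adverse event, but the condition behind it is reportable "unless the condition existed prior to the patient's MSC IMP injection".
- **Analysis set.** Section 13.3 evaluates general safety data on the safety analysis set. The entry under that heading covers patients who were injected. Sections 8.7 and 9.1 replace subjects who were not.

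Other sections plan to collect harvest harm. The calendar in 10.1 marks an adverse event assessment in the Obtain MSCs column. Its footnote 2, and section 9.10, require a call 3 ± 2 days after aspiration to ask about toxicity. Where the product fails to expand or fails testing, 9.1 has the subject "followed for 1 month post the aspiration procedure to ensure AE/SAEs are appropriately recorded".

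**The concern.** The product is autologous, so every subject must have a marrow aspiration before an injection is possible. Section 14.2 lists severe bleeding, infection that could spread and sedation effects among its risks. The primary objective is safety and tolerability, and section 5.4 justifies marrow over fat as the cell source partly by harvest adverse event rates (0.07% against 1.36 to 8.6%). Six subjects cannot confirm a rate of 0.07%, but the trial's harvest record should at least be complete.

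A recording rule with an undefined start and an exemption anchored to the injection, the later of the two procedures, can leave harvest events out. A reader of the final tables could not tell whether no harvest harm occurred or whether the rule did not keep it.

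**Working it through.** The plan has no figure to reproduce. The check is window arithmetic from the calendar in 10.1 and a side-by-side reading.

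**1. Harvest-to-injection interval.** Injection is day 0. Aspiration is day −28 ± 14: −28 − 14 = −42 and −28 + 14 = −14. The harvest therefore precedes injection by 14 to 42 days.

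**2. What the carve-out does in that interval.** Suppose an aspiration bleed or infection needs a procedure before day 0. The condition existed before injection, so the second bullet of 15.8 removes the duty to report it. The first bullet would keep the same event, because it applies whatever the attribution. The two bullets therefore conflict, and so does the second bullet with the assessment in 10.1 and the follow-up in 9.1. None of this depends on which blood draw is meant. Bruising, transient pain, nausea or drowsiness with no procedure stay outside the carve-out.

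**3. Which draw starts recording.** Three candidates fit the text:

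| Candidate | Where placed | Optional? | Order relative to aspiration |
|---|---|---|---|
| Laboratory panel at baseline | 10.1; 10.3, labelled as research | No; its tests supply eligibility values in 8.1 | Before (7.1 completes baseline first) |
| Banking sample at baseline | 10.1; 10.3, labelled as research; first option in 11.7 | Opt-in (12.3) | Before |
| Banking sample on the harvest day | 12.3; second option in 11.7 | Opt-in (12.3) | Possibly after (9.10) |

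The third row rests on 11.7, "Biobanking of participant blood will occur at a baseline visit or the day of the bone marrow aspiration"; on 12.3, where blood "will be collected from each participant on the day of bone marrow biopsy"; and on 9.10, "An IV will be placed for conscious sedation, if needed, and for blood collection following the aspiration procedure". Section 9.10 does not name the sample, so the order is possible, not established. If it applies, events during sedation and aspiration precede the window. On either banking reading, 12.3 adds a gap: "Subjects must opt into the biobanking aspect of the study by checking a box", so a subject who declines has no draw to start recording.

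**4. Who reaches the safety tables.** A subject aspirated but not injected is outside the set headed safety and is replaced. The one-month follow-up in 9.1 covers expansion or testing failure. Section 8.7 also foresees non-injection by the subject's choice, to which 9.1 does not extend, and the withdrawal visit in 10.5 is for discontinuation after injection. Section 13.7 lists all adverse event data by patient, but a listing is not a table with a denominator of aspirated subjects.

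**5. Scheduled contact in the interval.** The call falls 1 to 5 days after aspiration. From the call to the injection visit, the stretch with no scheduled adverse event contact runs from 14 − 5 = 9 to 42 − 1 = 41 days. The visit list in 10.3 shows only the aspiration itself at the harvest visit, whereas 10.1 marks an assessment there.

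**The case against.** The best defence is that the protocol collects harvest harm through several routes and that 15.8 is loosely worded. The assessment at the aspiration visit, the dedicated call and the follow-up after product failure are real. Section 15.3 defines an adverse event by its timing relative to participation in the research. Section 16.4 asks for any serious event to be reported immediately, related or not, although its timeline table is keyed to 30 days from injection. If the draw is a baseline one, recording starts before the harvest and agrees with the calendar. This version also describes the primary objective as achieved (5.5) and offers the six subjects a second injection (7.1) from stored cells without another aspiration, so rewording cannot change prospective capture for harvests already done.

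Much of that stands. It shows that the start point is ambiguous, not that it falls after the harvest. It does not rescue the carve-out, which conflicts with those other routes on any reading. Nor does timing remove the point: the main analysis follows the 24-month visits (13.1), so what is tabulated can still be corrected.

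A reader might infer more than the documents support:

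- *That every condition arising before injection is exempt.* Only a condition for which a procedure was done is.
- *That the safety tables will show no harvest harm because the rule excludes it.* The routes above collect it; the fault is unreliable capture.
- *That harvest events cannot be recorded because 15.5 attributes events only to the product.* Recording under 15.8 does not depend on attribution.
- *That the possible start dates, day −56 (earliest baseline, −42 − 14) to day −14 (latest aspiration), measure the defect.* That 42-day spread is mostly visit windows; baseline alone spans 28 days (−56 to −28).

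**Conclusion.** The point holds in limited form and should be acted on. The carve-out is a defect as written: over 14 to 42 days per subject it releases from reporting a harvest complication that needed a procedure. The start point is an ambiguity, with at least one reading that misses events during the aspiration.

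The loss from the safety tables rests on reading 13.3 by its headings. The labels there are crossed: the entry headed intention to treat describes the safety set as all enrolled patients, and under that reading aspirated-only subjects would be included. This needs settling either way.

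No number of lost events can be given, because the documents do not report how many subjects were aspirated without injection or what harvest events occurred. The dose-limiting toxicity endpoint is unaffected, since its window starts at injection.

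**What to change.** 1. In 15.8, start recording at consent or the first study procedure, in either case before the aspiration and independent of biobank consent.
2. In the second bullet of 15.8, tie the exemption for pre-existing conditions to that same point instead of the injection.
3. Reconcile 10.1, 10.3, 11.7, 12.3 and 15.8 on when blood is drawn, which draw is meant, and whether adverse events are assessed at the aspiration visit.
4. In 13.7, add one adverse event table for all aspirated subjects, injected or not, and apply it to the harvest events already collected, including those in replaced subjects.

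Separate attribution to the harvest in 15.5 would help reporting but is optional. The cost is protocol wording, a few more minor events to record and one extra table.

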16.0 DATA AND SAFETY MONITORING PLAN

16.1 Oversight and Monitoring Plan

The UWCCC Data and Safety Monitoring Committee (DSMC) is responsible for the regular review and monitoring of all ongoing clinical research in the UWCCC. A complete IND Study Monitoring Plan is located in the electronic records component of the Regulatory Binder for this IND. The IND Study Monitoring Plan describes the strategies, responsibilities, and quality management activities in place to ensure adequate protection of the rights, welfare, and safety of human subjects and the quality and integrity of the resulting data, in compliance with applicable laws, regulations, policies, and guidance. Quality management activities include both internal and external quality management processes used throughout the study, including but not limited to staff training, standardized

procedures, methods for data collection, study and data monitoring, and routine team meetings to review the study progress and isolate any compliance issues and/or trends. A summary of UWCCC DSMC activities is as follows:

- Reviews all clinical trials conducted at the UWCCC for subject safety, protocol compliance, and data integrity.
- Reviews all Serious Adverse Events (SAE) requiring expedited reporting, as defined in the protocol, for all clinical trials conducted at the UWCCC, and studies conducted at external sites for which the UWCCC acts as an oversight body.
- Reviews all reports generated through the UWCCC DSMS elements (Internal Audits, Quality Assurance Reviews, Response Reviews, Compliance Reviews, and Protocol Summary Reports) described in Section II of this document.
- Notifies the protocol PI of DSMC decisions and, if applicable, any requirements for corrective action related to data or safety issues.
- Notifies the CRC of DSMC decisions and any correspondence from the DSMC to the protocol Principal Investigator.
- Works in conjunction with the UW Health Sciences IRB in the review of relevant safety information as well as protocol deviations, non-compliance, and unanticipated problems reported by the UWCCC research staff.
- Ensures that notification of SAEs requiring expedited reporting is provided to external sites participating in multi-institutional clinical trials coordinated by the UWCCC.
- The decision to proceed with enrollment of a subject into the next higher dose group will be made by the study PI and the statistician after review of the AEs within the dose cohort

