- The DSMC will have oversight of the attribution of SAEs throughout the duration of the protocol.

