16.4 Expedited Reporting of Serious Adverse Events

- Depending on the nature, severity, and attribution of the serious adverse event, an SAE report will be phoned in, submitted in writing, or both according to the Table below.
 - Reporting of expedited and final SAE reports will go to:
 - 1)UWCCC DSMC via email at: [contact]
 - 2) [name], MD FRCP(C), UW Professor in Oncology, Assistant Dean for Therapeutics Discovery and Development, and Director of the Program for Advanced Cell Therapy, via email at: [contact]

Reporting to the UW IRB will be per IRB guidelines.

Determine the reporting time line for the SAE in question by using Table 3 below.

Phase 1 and Early Phase 2 Studies: Expedited Reporting Requirements for Adverse Events that Occur on Studies under an IND/IDE within 30 Days of the Last Administration of the Investigational Agent/Intervention ^{1,2}.

Table 4. FDA Reporting Requirements.

FDA Reporting Requirements for Serious Adverse Events (21 CFR Part 312)

NOTE: Investigators **MUST** immediately report to the UWCCC DSMC and any other parties outlined in the protocol ANY Serious Adverse Events, whether or not they are considered related to the investigational agent(s)/intervention (21 CFR 312.64).

An adverse event is considered serious if it results in ANY of the following outcomes:

- 1) Death.
- 2) A life-threatening adverse event (the patient was at risk of death at the time of the event; it does not refer to an event that hypothetically might have caused death if it were more severe).

- 3) An adverse event that results in inpatient hospitalization or prolongation of existing hospitalization for \geq 24 hours.
- 4) A persistent or significant incapacity or substantial disruption of the ability to conduct normal life functions.
- 5) A congenital anomaly/birth defect.
- 6) Important Medical Events (IME) that may not result in death, be life threatening, or require hospitalization may be considered serious when, based upon medical judgment, they may jeopardize the patient or subject and may require medical or surgical intervention to prevent one of the outcomes listed in this definition (FDA, 21 CFR 312.32; ICH E2A and ICH E6).

ALL SERIOUS adverse events within 30 days of IMP injection that meet the above criteria **MUST** be immediately reported to the UWCCC within the timeframes detailed in the table below:

Hospitalization	Grade 1 and Grade 2 Timeframes	Grade 3-5 Timeframes

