Resulting in hospitalization \geq 24 hrs	15 Calendar Days	24 Hour; 7 Calendar Days
Not resulting in Hospitalization \geq 24 hrs	Not required	

Expedited AE reporting timelines are defined as:

- **24-Hour; 7 Calendar Days** – The AE must initially be reported within 24 hours of learning of the AE, followed by a complete expedited report within 7 calendar days of the initial 24-hour report.
- **15 Calendar Days** – A complete expedited report on the AE must be submitted within 15 calendar days of learning of the AE

¹ Serious adverse events that occur more than 30 days after the last administration of investigational agent/intervention and have an attribution of probable or definite require reporting as follows:

Expedited 24-hour notification followed by complete report within 7 calendar days for:

- All Grade 3, 4, and 5 SAEs

Expedited 15 calendar day reports for:

- Grade 2 AEs resulting in hospitalization or prolongation of hospitalization

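### Capture of late adverse events in sections 15.8 and 16.4 does not match the attribution-free halting rules in 16.5, and the death halt differs between 9.7 and 16.5 (minor)

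*Combined protocol and SAP*

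**What the plan says.** **Recording (15.8).** All adverse events, whatever the attribution, "will be recorded from the time of the research blood draw through the 1 month post MSC injection visit". Beyond that point the duty is narrower: the event must be definitely, probably or possibly related "and is a CTCAE v5.0 grade 3 or higher, it will be reported regardless of the timeframe of the occurrence". The section does not say which injection the window refers to.

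**Expedited reporting (16.4).** Three statements bear on late SAEs:

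- The NOTE tells investigators to report to the DSMC at once "ANY Serious Adverse Events, whether or not they are considered related to the investigational agent(s)/intervention". The sentence has no time limit, but it stands below a table heading about events "within 30 Days of the Last Administration of the Investigational Agent/Intervention".
- The sentence that introduces the timeline table covers "ALL SERIOUS adverse events within 30 days of IMP injection that meet the above criteria".
- Footnote 1 deals with SAEs more than 30 days after the last administration and says that those that "have an attribution of probable or definite require reporting as follows". Possible attribution is left out.

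**Oversight (16.1).** The DSMC "Reviews all Serious Adverse Events (SAE) requiring expedited reporting, as defined in the protocol". Also, "The DSMC will have oversight of the attribution of SAEs throughout the duration of the protocol".

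**Halting (16.5 and 9.7).** Section 16.5 lists six events that halt enrollment and treatment pending DSMC and FDA review. Only the last, five or more SAEs of grade 3 or higher, requires at least possible relatedness. Section 9.7 repeats the list but limits the death halt to 30 days after injection.

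**The concern.** Five of the six halts ignore the investigator's causality judgment. The authors evidently knew how to add a relatedness condition, because they did so for the sixth. In a small first-in-human study this is sensible: a causality call on a single event is weak evidence, and a pattern may show only when a second like event occurs.

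The recording and reporting sections bring the causality call back once the first month is over. If staff follow 15.8 and footnote 1 literally, a late SAE labelled unrelated is neither required in the adverse event record nor sent to the DSMC as an expedited report. A rule such as two like SAEs at any time can then be applied only if someone remembers the first one. What is at stake is a halt on the injections still to be given. The primary endpoint is not affected, because dose-limiting toxicity is assessed within one month of injection.

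**Working it through.** There is no planned figure to reproduce. The check traces an event that occurs after the 1-month visit and is judged unrelated through each provision.

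| Halt in 16.5 | Attribution condition | Required by 15.8? | Required by the 16.4 NOTE, read without a time limit? | Required by 16.4 footnote 1? |
|---|---|---|---|---|
| Any death | None | No | Yes | No |
| Two of the same SAE, grade 3+ | None | No | Yes | No |
| Grade 3 SAE in first 3 subjects | None | No | Yes | No |
| Any event of grade 4+ | None | No | Only if serious | No |
| Hypersensitivity, grade 3+ | None | No, unless the 14.2 definition applies | Only if serious | No |
| Five or more SAEs, grade 3+ | At least possible | Rule not engaged | Rule not engaged | Rule not engaged |

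**Rows 1 to 3.** The outcome depends on how the NOTE is read. If it is unlimited, these events are reportable, but footnote 1 then says something different. If the 30-day heading limits it, 16.4 is consistent with itself, but late unrelated SAEs have no prompt route. Row 3 counts only if that rule extends to the contralateral substudy, which the protocol does not say.

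**Row 4.** Section 15.4 defines grade 4 as risk of death at the time of the event, and 15.6 makes a life-threatening event serious. Most grade 4 events are therefore SAEs. What remains is a grade 4 event judged unrelated and non-serious, for example a laboratory value on the 90-day blood count. Neither 15.8 nor the NOTE requires it, although 16.5 would halt on it.

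**Row 5.** Section 14.2 describes systemic hypersensitivity-like reactions as at least possibly attributable, which would bring a grade 3+ reaction within 15.8. But 14.2 speaks of the first 7 days, and 16.5 does not adopt its definition, so coverage is probable rather than certain.

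**Row 6.** For a late SAE judged possibly related, 15.8 and the NOTE (read without limit) require a report; footnote 1 does not.

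**Can a late event fall while there is still treatment to halt?** Yes. Under 7.1, contralateral injection is offered only after the 1-month objective has been met, so every subject is past the first-injection month when the second injections start. The 16.4 clock runs from the last administration, so it restarts at a subject's second injection; 15.8 is silent on this. Contralateral dates are not given. As an illustration only, suppose the 14-day stagger in 9.7 also applied to them: the fourth injection could come at 3 × 14 = 42 days, beyond day 40 (30 + 10, the end of the visit window) for the first subject. At the sixth, 5 × 14 = 70 days, the third subject (injected at 2 × 14 = 28) would be at 70 − 28 = 42 days.

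**Death halt.** A death at, say, day 60 after injection halts the study under 16.5 and does not under 9.7.

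**The case against.** The strongest reply is that the halts do not depend on reporting at all. Section 16.5 halts when the event occurs, with DSMC and FDA review to follow; no rule is conditioned on a 15.8 entry or an expedited report. This is one site, with adverse event assessment at every visit to 24 months (10.1, 10.3), weekly team meetings that discuss toxicity (16.2) and quarterly reports cumulating SAEs (16.2, 16.3). Other sections presuppose that unrelated SAEs are held: 15.11 sends them to the FDA annual report, 13.7 lists all adverse events, and 13.1 follows deaths to 24 months. The DSMC also oversees attribution. All of this stands, and it limits the practical effect.

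Second, 16.4 can be reconciled by treating the NOTE as the duty and the table and footnote 1 as timelines. That is a natural reading, but the text does not state it, and the NOTE's place under a 30-day heading points the other way. Even on that reading, footnote 1 sets no timeline for a late, possibly related SAE that 15.8 requires. The heading carries two footnote markers and only one footnote is visible, so some text may have been lost in reading the PDF.

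Third, all six first injections are done without a dose-limiting toxicity or SAE in the first month (5.5, 14.3). Only the optional second injections can still be halted, and once the last is given no treatment remains to be halted. This stands too.

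A reader might infer that a halt could wait for the next quarterly report, or that nearly the whole of each 24-month follow-up is unprotected. The documents support neither. The reporting interval bounds when the DSMC might first hear of an event, not when treatment stops. Follow-up time matters here only while an injection is still to be given.

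**Conclusion.** The mismatch is real and present in the current text. For late events judged unrelated, the 16.5 halts for any death and for two like SAEs rest on events that 15.8 does not require and that 16.4 may or may not require. The same is true of a grade 3 SAE in the first three subjects, if that rule reaches the substudy. A late, unrelated, non-serious grade 4 event is required by neither section. The two death halts differ; if both lists apply, the broader 16.5 version governs.

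Severity is minor. The exposure is limited to the contralateral phase, several other routes would probably bring such events to light, and no primary analysis or dose decision changes. The size cannot be put as a number of days, because the contralateral injection dates are not given. The conclusion assumes that contralateral injections remain to be given and that the IND Study Monitoring Plan cited in 16.1, which is not among the documents, does not already settle the point.

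**What to change.** - **15.8:** record all deaths, SAEs, events of grade 4 or higher and hypersensitivity reactions of grade 3 or higher, regardless of attribution, through the last visit. State that the full-recording window restarts at the contralateral injection.
- **16.4:** state that the table and footnote 1 set expedited timelines only and do not limit the NOTE. Add possible attribution to footnote 1, to agree with 15.8.
- **9.7:** adopt the 16.5 wording of the death halt. Section 16.5 requires FDA review before a stopping rule is changed, so plan for that step.

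The cost is an amendment with matching case report form wording, slight extra data entry for about six subjects, and the FDA review. The visits at which these events would be collected are already scheduled.
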